6.3. Windowing of Visits

All data will be categorized based on the scheduled visit at which it was collected. These visit designators are predefined values as used in the eCRF.

6.4. Withdrawals, Dropouts, and Loss to Follow-up

Time-to-event parameters will be censored if patients withdraw, drop out, or are lost to follow-up before documentation of the events (PD / death). Rules for censoring for PFS are detailed in Appendix 1.4.

7. STATISTICAL METHODOLOGY AND STATISTICAL ANALYSES

7.1. Statistical Methods

Whilst every effort has been made to pre-specify all analyses in this statistical analysis plan, if any additional exploratory analyses are found to be necessary, the analyses and the reasons for them will be detailed in the clinical study report (CSR).

7.1.1. Analysis for Time-to-Event Data

Time-to-event endpoints will be summarized using the Kaplan-Meier method [5] and displayed graphically when appropriate. Median event times and 2-sided 95% confidence intervals for each time-to-event endpoint [4] will be provided.

7.1.2. Analysis for Binary Data

Point estimates of binary endpoints will be provided for each treatment arm along with the corresponding 2-sided 95% confidence intervals using an exact method [3].

7.1.3. Analysis for Continuous Data

Descriptive statistics, such as the mean, standard deviation, coefficient of variation, median, minimum, and maximum values, will be provided for continuous endpoints. Linear or non-linear models may be employed to analyze the continuous data.

7.2. Statistical Analyses

In general, all data will be summarized by phase, arm, and assigned dose level (Phase Ib only), unless otherwise specified.

7.2.1. Standard Analysis

Study Conduct and Patient Disposition

Patient disposition includes the number and percentage of patients for the following categories: patients in each of the study populations, patients discontinued from the treatment, and primary reason to discontinue from the treatment. All percentages will be based on the number of patients in the ITT analysis set.

Demographic and Baseline Characteristics

- **Demographics:** Demographics will be summarized in a descriptive fashion in the ITT population. Baseline demographic data to be evaluated will include age, sex, race, ethnicity, height, weight, alcohol history, smoking history, and other parameters as appropriate. Patient enrollment by region and country may be summarized.
- **Baseline disease characteristics:** Eastern Cooperative Oncology Group [ECOG] performance status, cancer diagnosis and tumor stage at time of first pathologic diagnosis and at time of study entry.

Prior and Concomitant Medications

Prior and concomitant medications will be coded to ATC (Anatomical Therapeutic Chemical) classification and Drug Name using WHO Drug Dictionary (WHO-DD) (March 2016).

Medications that start and stop prior to the date of first treatment administration (either napabucasin or backbone, whichever is administered first) will be classified as ‘prior’ medications. If a medication starts on or after the date of first treatment administration up to the last dose date of study medication (inclusive), then the medication will be classified as ‘concomitant’. If a medication starts before the date of first treatment administration and stops on or after the date of first treatment administration, then the medication will be categorized as both a ‘prior’ and ‘concomitant’ medication.

Summaries of prior and concomitant medications will be provided by level 3 ATC classification and preferred term using frequencies and percentages for the ITT analysis set. A separate concomitant medications table using preferred base and level 4 ATC classification will also be provided using frequencies and percentages for the ITT analysis set.

Prior Cancer Treatment

Prior cancer treatment, including surgery, radiotherapy and hormone/biologic/chemotherapy/ other treatments will be summarized and/or listed for the ITT analysis set if available.

Medical History

Medical history will be coded using the Medical Dictionary for Regulatory Activities (MedDRA[®]) v19.0. Medical history will be summarized by system organ class (SOC) and preferred term (PT) using the number and percentage of patients for the ITT analysis set.

Duration of Overall Survival (OS) Follow-up

The duration of overall survival (OS) follow-up is defined as time from the date of randomization to either death or the last known visit alive. The median follow-up time for OS and the corresponding 95% confidence interval (using the method of Brookmeyer and Crowley, 1982 with the log-log transformation) will be summarized using the reverse Kaplan-Meier (KM) method for the safety set. The analysis involves the event and censoring rules to be switched (i.e., the patients who die become ‘censored’, and the censored patients are treated as the ‘event’).

Summaries of the number and percentage of patients who have died, those still in survival follow-up, those lost to follow-up, and those who have withdrawn consent will be also provided.

Extent of Exposure

Exposure may be summarized (per cycle and/or overall) as dose received (cumulative dose or actual dose intensity) or as dose received relative to the intended dose (relative dose [RD], or relative dose intensity [RDI]), or both.

The information that will be summarized depends on how the study drug is dosed (e.g., infusion cyclical, oral daily, oral cyclical).

Actual treatment duration = actual end of treatment date – date of first dose of study drug + 1

- For napabucasin, amcasertib, and sorafenib, the actual end of treatment date is the last dosing date

Cumulative dose in a cycle or overall is the sum of the actual doses received in a cycle or overall, respectively.

Intended cumulative dose in a cycle or overall is the sum of the intended dose level doses in a cycle or overall, respectively.

Actual Dose Intensity [DI]

- By cycle actual DI (*dose unit/day*) = [cumulative dose in the cycle] / [actual cycle duration in days]
- Overall actual DI (*dose unit/day*) = [overall cumulative dose] / [actual treatment duration in days]

Relative Dose Intensity (RDI): The basic intent is to evaluate dose per *time unit* factoring in dose reductions, interruptions, or delays.

Relative dose intensity (RDI) by cycle and overall:

- Intended DI (*dose unit/day*) = [intended cumulative dose per cycle] / [intended number of days in a cycle]
- By cycle RDI (%) = $100 \times$ [by cycle actual DI] / [intended DI]
- Overall RDI (%) = $100 \times$ [overall actual DI] / [intended DI]

Daily treatment compliance

Daily treatment compliance will be reported for each patient by phase, treatment arm and dose level cohort.

- The % of days the patient received full daily dose of napabucasin/amcasertib or sorafenib or higher out of actual treatment duration in days.
- The % of days the patient received a non-zero dose of napabucasin/amcasertib or sorafenib out of actual treatment duration in days.

Daily treatment compliance will be grouped according to the following categories: < 60%, ≥ 60% - < 80%, ≥ 80% - < 90%, ≥ 90%, and will be summarized for all arms.

These summaries will be performed for cycle 1 and overall.

7.2.2. Analysis for Primary Endpoint

7.2.2.1. Dose-Limiting Toxicity (Phase Ib)

7.2.2.2. Dose-Limiting Toxicity is the primary endpoint of the dose escalation component of the study, which will be summarized by treatment groups using the safety analysis set for patients in the dose escalation portion of the study. A listing of the DLTs will be provided. Objective Response Rate and Disease Control Rate

The ORR is defined as the percentage of patients with a BOR of CR or PR, and the DCR is defined as the percentage of patients with a BOR of CR or PR or SD. The categorizations of response (CR, PR, SD, PD, and NE) and the derivations of BOR are provided in Appendix 1.3.

ORR/DCR will be summarized for the ITT analysis set and repeated for the response evaluable analysis set as sensitivity analysis. ORR/DCR point estimates for each treatment arm will be provided along with the corresponding 2-sided 95% confidence intervals using an exact method [3].

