# 4.6 Criteria for Dose Escalation and Determination of Dose-Limiting Toxicity

Patients are considered evaluable for determination of DLT and for determination of dose-escalation if they have been exposed to at least 28 days of continuous daily administration of study drug (BBI608 or BBI503) in combination with sorafenib at a compliance level of at least 80% for the combination regimen.

Compliance for study drug (either BBI608 or BBI503) and sorafenib is calculated by dividing the number of pills ingested by the total number of pills assigned to be ingested (see Section 7.4). The assigned dose of BBI608 or BBI503 is that determined by the dose-level cohort into which the patient is enrolled. The assigned dose of sorafenib is the dose administered at the start of combination therapy, as determined during the 2-week run-in period. The starting dose of sorafenib is 400 mg twice daily, and dose-reductions according to standard of care are allowed. Events meeting DLT definition that occur during the sorafenib run-in period will not be considered DLTs. Events occurring at any time that are determined to be due solely to sorafenib will not be considered DLTs.

Enrollment at the next dose level of study drug (either BBI608 or BBI03) and/or enrollment of additional patients into the ongoing cohort will be based on the tolerability and safety observed in evaluable patients, according to criteria described below:

- If zero treated patients experience a DLT (defined below) by Day 28 of continuous daily dosing, then dose escalation will occur.
- If one treated patient experiences a DLT (defined below) by Day 28 of continuous daily dosing, then an additional three patients will be enrolled for a total of six patients treated at the same dose level. Escalation will occur if no additional DLTs are seen in that cohort (one of six patients).
- If two or more treated patients at a dose level experience a DLT (defined below) by Day 28 of continuous daily dosing, this will be the maximally administered dose.

Once the maximally administered dose is determined, a total of six patients will be treated at the previous dose level.

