## 4.7 **Dose-Limiting Toxicity**

Dose-Limiting Toxicity (DLT) is defined as the occurrence of any of the following toxicities possibly, probably, or definitely related to study drug (either BBI608 or BBI503) or to study drug in combination with sorafenib during the first 28 days of combination therapy, unless there is a clear alternative explanation:

- CTCAE (Common Terminology Criteria for Adverse Events) Grade 4 hematological toxicity.
- Grade 3 thrombocytopenia in the presence of active bleeding.
- Grade 3 or 4 non-hematological toxicity, except for Grade 3 nausea/vomiting/anorexia, diarrhea, or fatigue, symptoms that will be considered DLTs only if they persist more than seven (7) days despite optimal medical management. Grade 4 toxicity will be considered DLT.

Alopecia will not be considered a DLT. Assessment of DLTs will occur during the first 28 days of BBI608 or BBI503 therapy in combination with sorafenib. DLTs will be determined from both adverse events and changes from baseline in physical examination findings and laboratory parameters.

\* Once the amendment 3 is in effect, Arm 2 in the Phase II portion will be closed for enrollment.

The criteria for determination of DLTs will apply to a given administration schedule independently. Patients who discontinue protocol therapy for a reason other than a DLT may be replaced in order to fully evaluate a given dose-level.

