# 11.3 Removal, Replacement, or Early Withdrawals of Subjects

If a subject exits the study prior to receiving four weeks of study drug (either BBI608 or BBI503) for reasons other than a DLT, and is not evaluable for dose-escalation then another subject may be enrolled to replace the patient in order to fully evaluate safety and tolerability of a given dose-level.

If a subject exists the study after receiving four weeks of study drug (either BBI608 or BBI503), but before receiving an on-study objective disease assessment (and is therefore not evaluable for response), then that subject may be replaced.

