5.2. Safety Analysis Set

The safety population is defined as all patients who receive at least 1 dose of napabucasin, amcasertib, or sorafenib. The safety population will be used for all safety-related analyses such as AEs, laboratory tests, and vital signs.

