5.4. Dose Escalation Evaluable Analysis Set of Phase Ib

Patients are considered evaluable for the determination of dose escalation if they:

- a) Experience a DLT
- b) Complete 28 days of combination dosing at the assigned dose level

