7.2.4.1. Adverse Events

Overall Summary of AEs

An AE will be regarded as **treatment-emergent**, if:

- it occurs on the day of or after the first dose of napabucasin or amcasertib or a combination drug and up to 30 days after the last dose of any study drug; or
- it occurs prior to first dose date of napabucasin or amcasertib or a combination drug and worsens in severity on therapy and up to 30 days after the last dose of study drug.

Adverse events will be coded by SOC and PT using the MedDRA v19.0. The severity of AEs will be graded by the investigator using (NIH NCI CTCAE Version 4.0). The verbatim term will be included in the AE listings.

An overview of treatment-emergent adverse events (TEAEs) will be provided. The number and percentage of patients will be summarized for:

- Patients with at least one TEAE
- Patients with TEAEs of CTCAE Grade 3 or higher
- Patients with serious TEAEs
- Patients with napabucasin-related TEAEs

- Patients with napabucasin-related TEAEs of CTCAE Grade 3 or higher
- Patients with amcasertib-related TEAEs
- Patients with amcasertib-related TEAEs of CTCAE Grade 3 or higher
- Patients with sorafenib-related TEAEs
- Patients with sorafenib-related TEAEs of CTCAE Grade 3 or higher
- Patients with napabucasin-related serious TEAEs
- Patients with napabucasin-related serious TEAEs of CTCAE Grade 3 or higher
- Patients with amcasertib-related serious TEAEs
- Patients with amcasertib-related serious TEAEs of CTCAE Grade 3 or higher
- Patients with sorafenib-related serious TEAEs
- Patients with sorafenib-related serious TEAEs of CTCAE Grade 3 or higher
- Patients with TEAEs leading to napabucasin dose hold
- Patients with TEAEs leading to dose reduction of napabucasin
- Patients with TEAEs leading to amcasertib dose hold
- Patients with TEAEs leading to dose reduction of amcasertib
- Patients with TEAEs leading to sorafenib dose hold
- Patients with TEAEs leading to dose reduction of sorafenib

Summary of AEs during Run-in Period

Besides overall summary of AEs as described above, the analysis of AEs during Run-in period will be summarized separately. Run-in Period is defined from the first sorafenib dose date to one day prior to patient administrated the napabucasin/amcasertib, or to the end of treatment if patient discontinued the study treatment before the napabucasin/amcasertib administration. For Phase II sorafenib monotherapy arm patients, run-in period is defined as the first 14 days of sorafenib administration.

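### SAP 7.2.2.1 summarises DLT on the safety set, not the dose-escalation evaluable set, so a DLT proportion is too low at any dose level with both a DLT and a non-evaluable patient

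*SAP*

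**What the plan says.** SAP 7.2.2.1 names DLT as the primary endpoint of dose escalation, "which will be summarized by treatment groups using the safety analysis set for patients in the dose escalation portion of the study", and adds a listing of DLTs. It names no percentage or interval. SAP 7.1.2, however, plans point estimates with exact 95% intervals for binary endpoints in general.

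SAP 5.2 defines the safety set as "all patients who receive at least 1 dose of napabucasin, amcasertib, or sorafenib".

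SAP 5.4 defines a Dose Escalation Evaluable set through two conditions: experiencing a DLT, and "Complete 28 days of combination dosing at the assigned dose level". SAP 5.3 names the analyses that its response evaluable set serves, but SAP 5.4 names none. The set's only implied use is the count of patients in each study population under disposition (SAP 7.2.1).

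The protocol ties escalation to evaluable patients. Section 4.6 says that enrolment at the next dose level, or of more patients at the current one, "will be based on the tolerability and safety observed in evaluable patients". It also says: "Events meeting DLT definition that occur during the sorafenib run-in period will not be considered DLTs". Protocol 10.6 requires the numbers enrolled, with DLT and evaluable to be reported at each dose level by arm.

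**The concern.** The safety set can hold two kinds of phase Ib patient who are not evaluable for DLT.

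- **Run-in only.** Every patient starts with 14 days of sorafenib alone, and the first dose puts the patient in the safety set. The SAP foresees patients who go no further: its run-in period (SAP 7.2.4.1) extends up to the first napabucasin or amcasertib dose, "or to the end of treatment if patient discontinued the study treatment before the napabucasin/amcasertib administration". By protocol 4.6 these patients cannot contribute a DLT.
- **Early leavers.** Some patients may start combination therapy but leave before 28 days without a DLT. Protocol 4.7 provides for them: "Patients who discontinue protocol therapy for a reason other than a DLT may be replaced in order to fully evaluate a given dose-level". Protocol 11.3 says the same of a subject who leaves before four weeks of study drug "for reasons other than a DLT, and is not evaluable for dose-escalation then another subject may be enrolled to replace the patient". Each replacement makes the safety set at that dose level larger than the evaluable set.

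Both groups add to the denominator and never to the numerator. The primary-endpoint table would then rest on a different denominator from the one behind the escalation decisions, and a DLT proportion read from it could look lower than the one the investigators acted on.

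**Working it through.** **The plan's own DLT figures.** Protocol 10.5 and SAP 3.2.3 give the chance of escalating at true DLT rates p of 0.1 to 0.5. Under the 3+3 rule the chance is (1−p)³ + 3p(1−p)² × (1−p)³.

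| p | Computed | Stated |
|---|---|---|
| 0.1 | 0.906 | 91% |
| 0.2 | 0.709 | 71% |
| 0.3 | 0.494 | 49% |
| 0.4 | 0.309 | 31% |
| 0.5 | 0.172 | 17% |

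All five reproduce. The formula counts 3 or 6 patients, each with a known DLT outcome, which is the evaluable-patient denominator.

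**Inputs for the dilution.**
- x is the number of patients with a DLT at a dose level. Reading the two SAP 5.4 conditions as alternatives, every such patient is in both sets, so x is the same in each.
- E is the number evaluable: 3 to 6 by the cohort size in the protocol and SAP.
- k is the number of safety-set patients at that level who are not evaluable. The documents do not give k, so the range 0 to 3 is an assumption.

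**Formula.** The evaluable-set proportion is x/E and the safety-set proportion is x/(E+k). Their ratio is E/(E+k), whatever the value of x above zero.

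For E = 6 the factor is 6/7 = 0.857, 6/8 = 0.750 and 6/9 = 0.667 at k = 1, 2 and 3.

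| x of E | k = 0 | k = 1 | k = 2 | k = 3 |
|---|---|---|---|---|
| 1 of 6 | 16.7% | 1/7 = 14.3% | 1/8 = 12.5% | 1/9 = 11.1% |
| 2 of 6 | 33.3% | 2/7 = 28.6% | 2/8 = 25.0% | 2/9 = 22.2% |

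If the general rule of SAP 7.1.2 were applied, the exact 95% interval for 2 DLTs would move from 4.3–77.7% (2/6) to 3.7–71.0%, 3.2–65.1% and 2.8–60.0%.

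**Boundary cases.** With k = 0 the two sets give the same result. With x = 0 the proportion is 0% on either set, although an exact upper limit would be lower on the larger set.

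**The case against.** The strongest reply has four parts.

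1. Protocol 10.6 opens by summarising safety for all enrolled patients, and enrolment means the first sorafenib dose. A safety-set summary is therefore consistent with the protocol, and nowhere does the protocol require a DLT rate on the evaluable set. This stands in part. A reader might infer that the SAP breaches the protocol because the protocol's Study Drug Safety Population would leave out run-in-only patients, but that opening sentence does not support so strong a reading. The same section does, however, ask for the number evaluable by dose level and arm, and SAP 7.2.2.1 does not put it beside the DLT count.

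2. The numbers can be recovered. The disposition summary counts each population, SAP 7.2 sets a layout by phase, arm and assigned dose level, DLTs are listed, and the SAP is to be read with the protocol. This stands and lowers the weight. It also means that the evaluable set cannot be called wholly unused. It does not correct the denominator in the primary-endpoint table.

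3. The size is hypothetical. Protocol 3.3 expects 6 to 12 patients per arm over two planned dose levels, which is 6/2 = 3 to 12/2 = 6 per level and leaves little visible allowance for non-evaluable patients. SAP 7.2.2.1 also promises no percentage. Both are fair. The figures above are illustrations, although SAP 7.1.2 gives reason to expect a proportion.

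4. No decision changes. This stands in full. A reader might infer that diluted proportions could let a dose level pass as tolerable. The documents do not support that, because protocol 4.6 bases escalation on evaluable patients and the decision tables work from DLT counts.

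**Conclusion.** The point holds as a minor reporting matter. Followed as written, SAP 7.2.2.1 gives a DLT proportion that is too low by the factor E/(E+k) wherever a dose level has at least one DLT and at least one non-evaluable patient. For an assumed k of 1 to 3 with E = 6, that takes 33.3% to between 28.6% and 22.2%, and 16.7% to between 14.3% and 11.1%. The direction and the formula follow from the set definitions. The size rests on the assumed k and on a proportion being reported at all. Escalation, MTD and RP2D are not affected.

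One further inference should be resisted. Protocol 4.6 asks for at least 80% compliance before a patient counts as evaluable, while protocol 10.1 and SAP 5.4 state no compliance level. A reader might conclude that the present DLT denominator is ambiguous for that reason. It is not, because safety-set membership depends on neither 28 days of dosing nor compliance. The mismatch matters only once the evaluable set becomes the denominator.

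**What to change.** In SAP 7.2.2.1, summarise DLT by arm and assigned dose level on the SAP 5.4 set. Show the numbers enrolled, evaluable and with DLT in the same table, as protocol 10.6 requires. Keep the DLT listing on the safety set so that no patient drops out of view.

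As a consequence of adopting that set, reconcile its wording in protocol 10.1 and SAP 5.4, which give no compliance level, with protocol 4.6, which requires at least 80%. Otherwise the number evaluable could be counted in two ways. State also that the two conditions in SAP 5.4 are alternatives.

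The cost is one SAP paragraph, one table and the reconciled definition. No new data are needed.

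### SAP 7.2.2.1 summarises DLTs, the phase Ib primary endpoint, on the safety set, which can include patients unable to have a DLT, and leaves the evaluable set of SAP 5.4 unused

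*SAP*

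**What the plan says.** SAP 2.1 makes DLT the only phase Ib primary endpoint. The DLT paragraph of SAP 7.2.2.1 (printed under the number 7.2.2.2) describes DLT as an endpoint "which will be summarized by treatment groups using the safety analysis set for patients in the dose escalation portion of the study", and adds a listing. SAP 5.2 defines the safety set as "all patients who receive at least 1 dose of napabucasin, amcasertib, or sorafenib". SAP 7.2 states that "all data will be summarized by phase, arm, and assigned dose level (Phase Ib only), unless otherwise specified".

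Every phase Ib patient starts with 14 days of sorafenib alone (SAP 1.1). The DLT window is the first 28 days of the combination (Protocol 4.7). Protocol 4.6 adds: "Events meeting DLT definition that occur during the sorafenib run-in period will not be considered DLTs". Protocol 11.3 opens its replacement rule with "If a subject exits the study prior to receiving four weeks of study drug", limits it to exits for reasons other than a DLT, and allows another patient to be enrolled in that place.

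Protocol 4.6 bases escalation on what is seen in evaluable patients. SAP 5.4 defines a set for this purpose: patients who have a DLT, or who "Complete 28 days of combination dosing at the assigned dose level". Section 7 of the SAP attaches that set to no endpoint. Its only implied use is in the disposition table of SAP 7.2.1, which counts the patients in each population. Protocol 10.6 goes further and commits to reporting, for each dose level and arm, how many patients were enrolled, had a DLT and were evaluable.

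**The concern.** The denominator named for the primary endpoint is not the one on which doses were escalated. A patient who stops in the run-in is in the safety set, is tabulated at an assigned dose level of a drug never taken, and cannot contribute a DLT. A patient who leaves the combination early without a DLT was observed for only part of the window, and stays in the denominator alongside any replacement.

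Both kinds of patient add to the denominator and never to the numerator, so any error is towards apparent safety. What is at stake is how the phase Ib result reads in the study report: a DLT proportion lower than the one seen in the patients who supported the recommended dose.

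**Working it through.** **Inputs.** The analysis set is from SAP 7.2.2.1, its definition from SAP 5.2, the evaluable set from SAP 5.4, the DLT window and run-in exclusion from Protocol 4.6 and 4.7, and the limit of at most 1 DLT in 6 from SAP 3.2.2. The documents do not give the number of non-evaluable patients, *k*; values of *k* below are assumptions.

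**The plan's own figure.** SAP 3.2.3 gives escalation chances of 91%, 71%, 49%, 31% and 17% at true DLT rates 0.1 to 0.5. Under the 3+3 rule, P(escalate) = (1−p)³ + 3p(1−p)² × (1−p)³.

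- p = 0.1: 0.729 + 0.243 × 0.729 = 0.906
- p = 0.2: 0.512 + 0.384 × 0.512 = 0.709
- p = 0.3: 0.343 + 0.441 × 0.343 = 0.494
- p = 0.4: 0.216 + 0.432 × 0.216 = 0.309
- p = 0.5: 0.125 + 0.375 × 0.125 = 0.172

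All five reproduce. They describe decisions on cohorts of 3 and 6 and do not depend on which set SAP 7.2.2.1 names.

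**Who is in which set** (SAP 5.4(a) and (b) read as alternatives):

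| Patient | Safety set | SAP 5.4 set | Can count as a DLT |
|---|---|---|---|
| Has a DLT | yes | yes | yes |
| Completes 28 days of combination, no DLT | yes | yes | observed in full |
| Leaves the combination early, no DLT | yes | no | observed in part |
| Stops during run-in | yes | no | no |

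Every DLT is in both sets. With *x* DLTs in *n* evaluable patients, the safety-set proportion is x/(n+k) ≤ x/n, with equality when k = 0 or x = 0.

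**Size**, with the Clopper-Pearson 95% upper limit in brackets:

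| Evaluable result | k = 0 | k = 1 | k = 2 | k = 3 |
|---|---|---|---|---|
| 1 DLT in 6 | 16.7% (64.1%) | 14.3% (57.9%) | 12.5% (52.7%) | 11.1% (48.2%) |
| 2 DLTs in 6 | 33.3% (77.7%) | 28.6% (71.0%) | 25.0% (65.1%) | 22.2% (60.0%) |

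The second row is a level that fails the 1-in-6 limit.

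**How often k is at least 1.** If a share *q* of patients leave before 28 days of combination without a DLT, the chance that at least one accompanies *m* evaluable patients is 1 − (1−q)^m. For assumed q of 5%, 10% and 20%:

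- m = 6: 26%, 47%, 74%
- m = 3: 14%, 27%, 49%

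**The case against.** The best reply is Protocol 10.6. The SAP is to be read with the protocol (SAP 1), and the protocol already promises the DLT count and the evaluable count at each dose level by arm. The disposition table of SAP 7.2.1 also counts each population. This stands, and it limits the harm: a reader could rebuild the right proportion. It does not remove the point, because the SAP paragraph for the primary endpoint names a different set and does not carry the protocol's commitment over.

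Second, the plan does not expressly ask for a DLT rate. The paragraph asks for a summary and a listing, whereas the ORR and DCR text beside it asks for point estimates and exact intervals. SAP 7.1.2 says that "Point estimates of binary endpoints will be provided for each treatment arm along with the corresponding 2-sided 95% confidence intervals", but whether DLT falls under that general rule is an inference. This also stands, so the figures above apply only if a proportion is shown.

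Third, the shifts are small beside the interval widths, and a level with no DLT reads 0% on either set. True, though the shifts run one way.

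Fourth, the escalation bullets in Protocol 4.6 count treated patients, so the basis is less tidy than it might be. The sentence introducing them, however, ties escalation to evaluable patients.

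A reader might go further and infer that the diluted rate could mislead a change of the recommended dose during phase II, which Protocol 4.3 permits. The documents do not support that. The SAP governs the study report, which comes at the end (Protocol 13.12), no formal interim analysis is planned (SAP 4), and nothing links this table to such a decision.

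**Conclusion.** The concern holds as a matter of reporting. SAP 7.2.2.1 puts the phase Ib primary endpoint on a set that can include patients who could not have a DLT or were not observed for the full window, and the set built for the purpose goes unused. A DLT proportion on the safety set is equal to or lower than the evaluable proportion: 1/6 (17%) reads 14% or 13%, and 2/6 (33%) reads 29% or 25%, with one or two non-evaluable patients assumed.

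The one-way direction rests on SAP 5.4(a), which keeps every patient with a DLT in the evaluable set. The size rests on an assumed number of early exits; with none there is no effect. DLT counts, the listing and the dose decisions do not depend on this denominator, and the recommended dose also rests on pharmacokinetics and on toxicity beyond the first cycle (Protocol 4.2). It would be wrong to read this as a finding that the escalation itself was unsound.

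**What to change.** In SAP 7.2.2.1 write: *DLTs will be summarised on the dose escalation evaluable set (Section 5.4), by arm and assigned dose level, giving the number enrolled, the number with a DLT and the number evaluable. If a rate is shown, it will have an exact 95% CI.* Keep the safety set for the adverse event tables and the DLT listing.

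State which evaluability definition was applied. Protocol 4.6 requires exposure "at a compliance level of at least 80% for the combination regimen"; Protocol 10.1 and SAP 5.4 do not. The inconsistency is within the protocol, so adding the condition to SAP 5.4 alone would only move the mismatch. If the condition is used, attach it to 5.4(b) only, so that no patient with a DLT drops out.

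As an editorial correction, SAP 2.1 should cite Protocol 4.7 for the DLT definition; the protocol has no section 3.10.

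The cost is one changed denominator and a sentence or two of text. The counts are already promised. The downside is smaller denominators and wider intervals on cohorts of 3 to 6. Applying the 80% condition would also need a derivation: Protocol 4.6 counts pills over 28 combination days that span cycles 1 and 2, whereas SAP 7.2.1 measures compliance in days for cycle 1 and overall.
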